1.4 Relevant Literature and Data

The goal of this project is to evaluate a novel transdiagnostic treatment for anhedonia. Anhedonia, the loss of motivation and pleasure for enjoyable activities, is a transdiagnostic symptom associated with significant functional deficits in social and occupational domains (Kwapil, 1998). In mood disorders, anhedonia is associated with risk for future depressive episodes (Wardenaar, Giltay, van Veen, Zitman, & Penninx, 2012), a more chronic illness course (Spijker, Bijl, de Graaf, & Nolen, 2001), and poorer treatment response to both pharmacologic (McMakin et al., 2012) and neurostimulation (Downar et al., 2014) interventions. Outside of mood disorders, anhedonia is associated with greater risk of anxiety disorders (Kashdan, Elhai, & Frueh, 2006) and reduced cognitive and social functioning as well as quality of life (Herbener, Harrow, & Hill, 2005; Kashdan, Weeks, & Savostyanova, 2011; Pietrzak et al., 2015; Rey, Jouvent, & Dubal, 2009). Across psychiatric disorders, deficits in approach motivation (reduced reward valuation and willingness to work for rewards) and initial response to rewards (reduced hedonic responses to pleasurable stimuli) have been proposed to subserve anhedonic symptoms by reducing approach behaviors and pleasurable experiences, as well as subsequent opportunities for positive reinforcement (Keller et al., 2013; Treadway & Zald, 2013).

The mechanistic objective of this proposal is to explicate the brain-behavior relations between anhedonia and the dimensional constructs of approach motivation and initial responsiveness to reward. This will be achieved by measuring mesocorticolimbic target engagement before and after BATA treatment. In our previous collaborative work (MH094781 & MH078145) we delineated the neurobiological mechanisms of deficits in these dimensional RDoC constructs, including altered mesocorticolimbic activation that subserves approach behaviors towards biologically meaningful goals and hedonic responses to pleasurable stimuli (Dichter, Kozink, McClernon, & [name], 2012; Felder et al., 2012; Schiller, Minkel, [name], & Dichter, 2013; [name] et al., 2009; [name], Rittenberg, & Dichter, 2011), changes in activation of these brain regions after behavioral activation psychotherapy (Dichter et al., 2009; Dichter, Felder, & [name], 2010), and linkages between functioning of mesocorticolimbic systems and behavioral activation treatment outcomes (Crowther et al., 2015; Dichter et al., 2015). The goals of this proposal are to extend these lines of inquiry into first an experimental therapeutics study (R61 phase) and then a clinical trial (R33 phase) in a transdiagnostic sample characterized by anhedonia.

2 STUDY OBJECTIVE

2.1 Primary Objective

Aim 1: To evaluate whether BATA produces changes in neural responses to reward anticipation and reward outcomes using high field fMRI that exceed our a priori target engagement criteria (right caudate nucleus (CN) activation during reward anticipation and decrease rostral anterior cingulate cortex (rACC) activation during reward outcomes) and exceed changes due to MBCT, an active comparison treatment.

2.2 Secondary Objective

Aim 2: To evaluate the effects of BATA versus an active comparison treatment on anhedonic symptoms.

3 INVESTIGATIONAL PLAN (brief overview)

3.1 Study Design

Randomized, parallel design.

Study phases:

- (1) Phone/online Screening: initial screening for eligibility.
- (2) In-person Screening: further screening for eligibility and consent
- (3) Baseline fMRI
- (4) Initiate up to approximately 15 weeks of therapy (experimental treatment (BATA) or comparison treatment (MBCT))
- (5) Mid-treatment fMRI scans at approximately weeks 8 and 12.
- (6) Post-treatment fMRI scan

3.2 Allocation to Treatment Groups and Blinding (if applicable)

Patients will be assigned randomly to the experimental treatment (BATA) or comparison treatment (Mindfulness Based Cognitive Therapy (MBCT)). Groups will be stratified based on lower (20-30) and higher (31+) SHAPS scores. Stratification will be conducted by the study statistician using a computerized randomization procedure.

3.3 Study Duration, Enrollment and Number of Subjects

Study duration: Approximately 16 weeks.

3.4 Study Population

Inclusion Criteria

- 1) 18-50 years old and treatment seeking;
- 2) SHAPS scores ≥ 20 , corresponding to clinically significant anhedonia;
- 3) Clinician's Global Impression Scale-Severity score (CGI-S) ≥ 3 to assure a clinically impaired sample;
- 4) Seeking treatment for anhedonia (i.e., referred from an outpatient clinic or responded to an advertisement for anhedonia treatment; endorses desire for treatment during screening).

Exclusion Criteria

- 1) Those for whom medication management is the primary gold-standard treatment, including those with bipolar disorder/mania, schizophrenia spectrum, and other psychotic disorders;
- 2) Prior treatment with behavioral activation therapy for depression or mindfulness-based treatments (those

- with exposure to other forms of psychotherapy, e.g., supportive therapy, will be eligible);
- 3) Those who may have difficulty understanding the cognitive components of BATA, including those with intellectual disability, neurocognitive disorders, and dissociative disorders;
 - 4) Feeding and eating disorders which may have confounding effects on the BOLD fMRI signal;
 - 5) Substance Use Disorders given confounding effects of substances of abuse on the BOLD fMRI signal;
 - 6) Suicidal intent and plan;
 - 7) Psychotropic medication use in the past 4 weeks (8 weeks for fluoxetine) and/or current psychotherapy. Participants must be medication-free at study entry; study personnel will not supervise medication taper for the purpose of the study, but those who taper under the supervision of their regular provider will be eligible;
 - 8) Currently pregnant, as measured by urine pregnancy screen immediately before MRI scans;
 - 9) Positive urinalysis screen for cocaine, marijuana, opiates, methadone, amphetamines, and benzodiazepines (conducted on-site via Biosite Triage Meter Plus) at study entry.
 - 10) No neurological conditions (e.g., history of stroke, seizure, or TBI);
 - 11) Contraindications for 7T imaging (criteria are more stringent than for 3T imaging): Metal in the body, dental work that is not fillings or gold, any tattoos, any metal in the body, any metal injury – especially those to the eyes, any other type of implant unless they are 100% plastic.

4 STUDY PROCEDURES (what will be done)

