Suicidality: As with any study that utilizes samples that may include participants with mood disorders, there is the potential risk that a participant's mood may worsen, and/or that a participant may become suicidal. PI [name] and the rest of the CBRTTP staff have extensive experience working with suicidal populations. Suicidal ideation will be assessed at the initial interview and self-report session and as indicated throughout the study. Suicidal ideation will be assessed at each research assessment session and as indicated throughout the study using the Columbia-Suicide Severity Rating Scale (C-SSRS) screening interview. Participants indicating "yes" on items 4 (Active Suicidal Ideation with Some Intent to Act, without Specific Plan) and/or 5 (Active Suicidal Ideation with Specific Plan and Intent) within the last week will be excused from the trial and referred to more intensive clinical management. As a part of that risk assessment and plan, an ideographic safety plan will be developed that may include a safety contract, referral for further outpatient treatment, and/or inpatient hospitalization.

Incidental Findings: On rare occasions, a participant may exhibit a frank abnormality on their research MRI scan as noted by the research MRI technician. In consultation with our Office for Risk Management, we have developed the following protocol for these infrequent events: (1) the MRI technician will inform the center director and/or associate director and the PI of the finding, and they will evaluate the images for technical artifacts; (2) if no technical artifacts are present, the anatomical images will be examined by a neuroradiologist who will evaluate the images and provide a follow-up recommendation. Because images are not of clinical quality, a definitive diagnosis is not possible; (3) If the incidental finding is within normal limits, no further action will be taken. (4) If the finding is not within normal limits, the participant will be contacted by phone by the PI and will given a letter that provides additional explanation and reference materials. The PI will follow-up by telephone to ensure that the process has been completed and that the participant does not have further questions.

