4.2 Intervention/Treatment procedures (by visits)

BATA and MBCT Groups:

	Screening Day -14 to -1	Enrollment/Baseline Visit 1, Day 1	Study Visit 2 Day 7 +/-7 days (therapy session #1)	Study Visit 3 Day 14 +/-7 days (therapy session #1)	Study Visit 4 Day 21 +/-7 days (therapy session #2)	Study Visit 5 Day 28 +/-7 days (therapy session #3)	Study Visit 6 Day 35 +/-7 days (therapy session #4)	Study Visit 7 Day 42 +/-7 days (therapy session #5)	Study Visit 8 Day 49 +/-7 days (therapy session #6)	Study Visit 9 Day 56 +/-7 days (therapy session #7)	Study Visit 10 Day 63 +/-7 days (therapy session #8)	Study Visit 11 Day 70 +/-7 days (therapy session #9)	Study Visit 12 Day 78 +/-7 days (therapy session #10)	Study Visit 13 Day 85 +/-7 days (therapy session #11)	Study Visit 14 Day 92 +/-7 days (therapy session #12)	Study Visit 15 Day 99 +/-7 days (therapy session #13)	Study Visit 16 Day 106 +/-7 days (therapy session #14)	Study Visit 17 Day 113 +/-7 days (therapy session #15)	Study Visit 18 Day 114 +/-14 days	Final Study Visit 19 Day 115 +/-14 days
Procedures																				
Informed consent and baseline symptom measures	X																			
fMRI scan (includes urine pregnancy test and fMRI safety screen)		X						X				X								X
Randomization		X																		
Administer study intervention			X	X	X	X	X	X	X	X	X	X	X	X	X	X	X	X	X	
SHAPS		X							X			X							X	X

Questionnaires and safety assessments:

- 1) Columbia-Suicide Severity Rating Scale (C-SSRS) completed if a subject endorses suicidal thoughts at therapy visits.
- 2) 7T safety screening completed immediately before each scan.
- 3) SHAPS completed at pre-treatment, week 8, week 12, and immediately post-treatment.

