5.3 Safety Evaluations

- 1) 7T MRI safety screening form
- 2) Pregnancy tests prior to each fMRI for women of childbearing potential
- 3) Columbia-Suicide Severity Rating Scale (C-SSRS), administered if the subject expresses any suicidality or thoughts that are concerning to the therapist.
- 4) If a participant reports any significant distress or refusal during the diagnostic interview session, he or she will be withdrawn immediately. If a participant reports any significant distress or refusal during the brain imaging session, he or she will be withdrawn immediately.
- 5) If a participant reveals information that they did not reveal during the screen that prevents them from participating (e.g., metallic device), or if tests positive for urine pregnancy screen, if female, they will be withdrawn from the study.

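### The entry exclusion, the removal rule and the C-SSRS timing for suicidality do not agree across sections and need to be reconciled

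*Combined protocol and SAP*

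**What the plan says.** **Entry.** The exclusion criteria in the synopsis and in section 3.4 carry the same entry: "Suicidal intent and plan".

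**Removal.** Section 1.3 (Potential Risks, Suicidality) acts on a yes to C-SSRS "items 4 (Active Suicidal Ideation with Some Intent to Act, without Specific Plan) and/or 5". Such participants "within the last week will be excused from the trial and referred to more intensive clinical management". Section 1.3 (Protections Against Risk, Treatment/Suicidality) adds a second removal wording, for a marked worsening of psychiatric symptoms, suicidality among them, and gives no threshold. The same paragraph requires that anyone who reports suicidal intent be assessed at once under a separate risk protocol.

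**Timing of the C-SSRS.** Section 1.3 states: "Suicidal ideation will be assessed at each research assessment session and as indicated throughout the study using the Columbia-Suicide Severity Rating Scale". The synopsis (Safety Evaluations) and the list under the visit table in section 4.2 have it "completed if a subject endorses suicidal thoughts at therapy visits". Section 5.3, the general list of safety evaluations, has it "administered if the subject expresses any suicidality or thoughts that are concerning to the therapist". The in-person screening and pre-treatment scan procedures in section 4.1, the visit table in section 4.2, and the description of scan sessions at the end of section 4.2 mention no routine C-SSRS.

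**The concern.** The entry rule and the removal rule use different thresholds, so one person can pass the first and meet the second. The removal rule is also written in terms of answers to two numbered C-SSRS items, while the sections that tell staff what to do at each visit do not schedule the instrument that produces those answers.

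Patient safety comes first here: section 1.3 itself names suicidality as a risk in this population. The second stake is consistent conduct. Therapy takes place at one institution and scanning at another, and staff working from different sections could reach different eligibility, screening and removal decisions for the same patient. The third is data: a participant removed after randomisation may contribute no post-treatment fMRI or SHAPS value, and those are the primary and secondary endpoints.

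**Working it through.** The plan gives no figure on this point, so there is nothing to reproduce or compute. The check is a comparison of the texts.

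**Step 1: thresholds.** Take the possible answers to C-SSRS items 4 and 5 for the last week.

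| Candidate | Entry list (synopsis, 3.4), read literally | Removal rule (1.3, Suicidality) |
|---|---|---|
| Neither item | Not excluded | Not removed |
| Item 4 yes, item 5 no (intent, no specific plan) | Not excluded | Removed |
| Item 5 yes (plan and intent) | Excluded | Removed |

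The rules agree in the first and third rows and disagree in the second. The removal rule covers intent with a plan as well, so the mismatch is only for intent without one. The second removal wording in section 1.3 cannot be placed in the table because it has no threshold.

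**Step 2: timing.** Take a research visit, for example a scan, at which the participant says nothing about suicidality.

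| Source | Is a C-SSRS called for? |
|---|---|
| 1.3, Suicidality | Yes, if the visit is a research assessment session |
| 5.3 | No, because its condition is not met |
| 4.2, visit table and scan-session contents | Not listed |
| Synopsis and safety list in 4.2 | Silent, because they speak of therapy visits |

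Sections 1.3 and 5.3 give different answers. The synopsis and the list in 4.2 do not by themselves contradict section 1.3, since they address another setting. The term research assessment session is not defined, so the documents do not settle which visits section 1.3 covers.

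**Step 3: the two together.** The removal rule needs the answers to items 4 and 5. Under sections 4.1, 4.2 and 5.3 as written, those answers exist only for participants in whom something has already prompted a C-SSRS. Staff working from these sections could complete screening and the scan visits without the information that the rule in section 1.3 requires.

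**The case against.** The best case for the plan is that section 1.3 closes most of the gap. It has ideation assessed at the initial interview, and if that interview counts as a research assessment session, a candidate with item 4 positive is identified before randomisation. The synopsis also places randomisation after the baseline scan, which gives another chance. An exclusion list and a discontinuation rule may legitimately differ, and the entry criterion might be meant as two separate features. Anyone who reports intent, with or without a plan, is to be assessed immediately. On timing, routine use at research visits and triggered use at therapy visits are compatible, and section 5.3's mention of the therapist hints that it too has therapy contacts in mind. Absence from the visit table is weak evidence: the SCID5, the CGI-S and the urine drug screen have no row of their own either, and section 4.1 omits the CGI-S and the drug screen although both decide eligibility.

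Much of this stands. A reader might infer that patients will be randomised under one rule and removed at once under the other. The documents do not support that as a certainty, because the initial-interview assessment may intervene. A reader might also infer that patients who do not volunteer suicidal thoughts go unscreened. The texts speak of endorsing or expressing thoughts and of therapist concern, which is compatible with being asked, and the trigger operates across the whole series of therapy visits.

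The rest does not dispose of the point. Neither eligibility list refers to section 1.3, and nothing says that the entry criterion means either feature alone. Section 5.3 is a general safety list that is not confined to therapy visits, and it states a condition, which is more than an omission. The two-settings reading is plausible, but the protocol does not state it.

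**Conclusion.** The concern holds as an inconsistency between stated rules. Read literally, the entry criterion is narrower than the removal rule for one group, those with intent but no specific plan. The routine C-SSRS in section 1.3 is at odds with the conditional one in section 5.3 and is not carried into the visit procedures.

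This rests on reading the entry criterion as a conjunction and section 5.3 as applying to all visits. Both are the plain readings, though neither is the only one possible. How often the mismatch would matter cannot be given: the documents report no rate of item 4 answers, and the number of visits at which section 1.3 would require a C-SSRS depends on an undefined term. Removals for suicidality that emerges during treatment would occur whatever the entry wording, so that loss of data is not attributable to this mismatch. The power statement in section 6.5 is untouched. The matter should be corrected because it bears on patient safety and is cheap to resolve.

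**What to change.** Reconcile the exclusion criteria and Safety Evaluations in the synopsis, both suicidality paragraphs in section 1.3, and sections 3.4, 4.1, 4.2 and 5.3, so that:

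- the entry threshold and the removal threshold agree, or any intended difference is stated;
- the second removal wording in section 1.3 is tied to the same rule or given its own definition;
- research assessment session is defined by naming the visits it covers;
- one statement of C-SSRS timing is used throughout, distinguishing research from therapy visits if that is the intention, and appears in the visit table.

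Which threshold and which timing apply is for the sponsor's clinicians; this review takes no position. The cost is protocol wording and, if the per-session rule is kept, a brief interview at visits already scheduled.

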4.1 Screening/Baseline Visit procedures

Phone/online Screening: fMRI and medication contraindications will be assessed; SHAPS will be administered.

In-person screen: fMRI and medication contraindications assessed; SHAPS administered; SCID5 administered.

Randomization: Randomization will be completed by the study statistician based on a pre-registered randomization schedule.

Scan Sessions (pre-treatment): 7T MRI safety screening form; urine pregnancy test for women; Structural and functional MRI scans will be collected.

4.2 Intervention/Treatment procedures (by visits)

BATA and MBCT Groups:

	Screening Day -14 to -1	Enrollment/Baseline Visit 1, Day 1	Study Visit 2 Day 7 +/-7 days (therapy session #1)	Study Visit 3 Day 14 +/-7 days (therapy session #1)	Study Visit 4 Day 21 +/-7 days (therapy session #2)	Study Visit 5 Day 28 +/-7 days (therapy session #3)	Study Visit 6 Day 35 +/-7 days (therapy session #4)	Study Visit 7 Day 42 +/-7 days (therapy session #5)	Study Visit 8 Day 49 +/-7 days (therapy session #6)	Study Visit 9 Day 56 +/-7 days (therapy session #7)	Study Visit 10 Day 63 +/-7 days (therapy session #8)	Study Visit 11 Day 70 +/-7 days (therapy session #9)	Study Visit 12 Day 78 +/-7 days (therapy session #10)	Study Visit 13 Day 85 +/-7 days (therapy session #11)	Study Visit 14 Day 92 +/-7 days (therapy session #12)	Study Visit 15 Day 99 +/-7 days (therapy session #13)	Study Visit 16 Day 106 +/-7 days (therapy session #14)	Study Visit 17 Day 113 +/-7 days (therapy session #15)	Study Visit 18 Day 114 +/-14 days	Final Study Visit 19 Day 115 +/-14 days
Procedures																				
Informed consent and baseline symptom measures	X																			
fMRI scan (includes urine pregnancy test and fMRI safety screen)		X						X				X								X
Randomization		X																		
Administer study intervention			X	X	X	X	X	X	X	X	X	X	X	X	X	X	X	X	X	
SHAPS		X							X			X							X	X

Questionnaires and safety assessments:

- 1) Columbia-Suicide Severity Rating Scale (C-SSRS) completed if a subject endorses suicidal thoughts at therapy visits.
- 2) 7T safety screening completed immediately before each scan.
- 3) SHAPS completed at pre-treatment, week 8, week 12, and immediately post-treatment.

Behavioral Activation Treatment for Anhedonia (BATA): We have modified Behavioral Activation Treatment for Depression to create Behavioral Activation Treatment for Anhedonia (BATA) which we will evaluate in this study. Treatment will consist of ~15 weekly 45-minute sessions. Session 1 provides orientation and psychoeducation on anhedonia, and activity monitoring is introduced. Sessions 2-3 include structured values assessments of 10 life areas (e.g., Family Relationships, Employment/Career) to enhance motivation for sustained behavior change and to clarify goals. Following goals clarification, an activity hierarchy is developed, establishing a set of idiographic behavioral targets across life areas prioritized by ease of implementation to scaffold task engagement during the course of treatment. Session 4 focuses on reduction of avoidance. Sessions 5 and above assess completion of goals from the previous sessions, troubleshoot barriers to goal completion, and assign goals for the coming weeks. Inherent in this structure is therapist assistance in setting achievable goals, which is often impaired in the context of anhedonia. Embedded in the review of goal completion is heightened awareness of anhedonia and identification of behaviors that are associated with greater positive response in the form of subjective importance and enjoyment. Those behaviors then form the basis of goals for the following weeks. The therapist uses motivational techniques to elicit goal-directed behaviors outside session including tying goals to the patient's identified values, open-ended questioning and reflective listening, and functional analysis to select behaviors maximally likely to achieve the patient's goals. Increased positive affect and decreased negative affect are theorized to result from increased contact with potential reinforcers through reduced behavioral avoidance. Maladaptive behaviors such as avoidance decrease the effectiveness of positive events in shaping future behavior, weakening the learned association between adaptive behaviors and positive outcomes. In this way, the overarching goal of BATA is to encourage the patient to engage in activities that increase contact with personally relevant, values-consistent reinforcers, thereby strengthening links between environmental engagement, positive mood, and future approach-oriented behaviors. Several specific new components are included in BATA: in Session 1, content specific to depression is removed and additional psychoeducation about anhedonia and response to rewards is provided. This includes education about anticipatory versus consummatory anhedonia, positive versus negative reinforcement, and how anhedonia can foster avoidance. Activity monitoring is streamlined to reduce monitoring effort for low-motivation patients. Sessions 5 includes a focus on increased frequency of initiation of new behaviors to target motivation. In Session 6, once novel behaviors are established, additional exercises will be introduced to increase present-moment savoring as a means to target pleasure.

Psychotherapy sessions:

Both BATA and MBCT groups: up to 15 weekly 45-minute individual psychotherapy sessions

Scan sessions:

Both BATA and MBCT groups: scans will occur at week 8, week 12, and week 15 (final week): these will include administering the 7T MRI safety screening form, a urine pregnancy testing for women, and structural and functional MRI scans will be collected.

